6.1. Primary outcome

6.1.1. 100 day mortality.

100 day mortality is chosen as the primary outcome because this is a preliminary study designed to provide data necessary to plan a prospective comparative study of transplant and non-transplant therapy. The rationale for use of HCT for MDS in patients ≥ 65 years old is that outcomes are thought to be similar to those in adults 55-64, where HCT is an accepted therapy, given similar non-age-based eligibility criteria are met¹¹. This study will determine, in a large cohort of patient ≥ 65 years old, whether early mortality is indeed in the range expected and will also provide information on prognostic factors for this outcome.

6.2. Secondary outcomes

6.2.1. Acute GVHD: Occurrence of grade II, III and/or IV skin, gastrointestinal or liver abnormalities fulfilling the IBMTR criteria for acute GVHD.

6.2.2. Chronic GVHD: Occurrence of symptoms in any organ system fulfilling the criteria of chronic GVHD.

6.2.3. Relapse: disease recurrence or persistent disease for patients not in CR at transplant. Those who survive without recurrence or persistent disease are censored at the date of last contact.

6.2.4. Progression: increase in marrow blasts to $> 20\%$; patients without progression are censored at time of most recent marrow examination.

6.2.5. Disease-free survival: survival without death or relapse. Those who survive without recurrent or persistent disease are censored at the date of last

contact.

6.2.6. Progression-free survival: survival without increase in marrow blasts to >20%; patients without progression are censored at time of most recent marrow examination.

6.2.7. Overall survival: Surviving patients are censored at the date of last contact.

7.0 DATA COLLECTION:

All data necessary for this study will be collected using the existing mechanisms of the CIBMTR under, operating under the “NMDP and CIBMTR Protocol for a Research Database for Hematopoietic Stem cell Transplantation and marrow Toxic Injuries”, version 6.0, (NCT01166009) (Appendix A). The Informed Consent for this protocol is also found in Appendix A. These data collection mechanisms support the reporting required for the Stem Cell Therapeutic Outcomes Database (SCTOD), and the research endeavors of the CIBMTR. Existing data instruments and procedure manuals can be found at www.cibmtr.org/DataManagement. Registration of patients and submission of data will follow standard CIBMTR procedures.

8.0 STUDY DESIGN:

This study initially had a target accrual of 240 patients older than age 65 for the 100 day mortality primary endpoint. Sample sizes were based on an inferiority test of the hypothesis that the 100 day mortality rate in the ≥ 65 year old cohort is higher than 20%, the approximate 100-day mortality rate in a 55-64 year old cohort¹². The study was designed to have approximately 80% power to detect a 6.5 % or greater increase in 100 day mortality rate in the ≥ 65 year old cohort. Table 1 below shows the power of the test for various 100 day mortality rates.

Table 1.	
True 100 day mortality rates	Power
0.21	10%
0.22	20%
0.23	32%
0.24	46%
0.25	60%
0.26	73%
0.27	83%
0.28	90%
0.29	94%

At each of the four evaluations points, we will prepare descriptive tables of the covariates. Kaplan-Meier estimates of mortality and disease free survival will be

constructed for the entire cohort and by sub-groups defined by the fixed covariates such as IPSS score. Cumulative incidence curves will be constructed to estimate acute GVHD incidence, relapse progression rates. These analyses will be conducted when 60, 120, 180 or 240 patients have at least 100 days of potential follow-up. As they are descriptive in nature, no p-values are computed until the entire cohort has been observed.

When accrual of the first 240 patients is complete and all patients have been followed for at least 100 days, the association between outcomes and the variables listed in Section 3.0 will be examined in either a logistic regression model or a Cox proportional hazards model depending on the outcome of interest. Forward stepwise model selection techniques will be used in this approach. These analyses will include a cohort of patients ages 55-64 years transplanted for MDS and related disorders in the same centers as the CMS beneficiaries included in this analysis.

After accrual is complete, follow-up of this cohort will continue, through standard CIBMTR mechanisms, after completion of these analyses. Evaluation of all secondary endpoints will be repeated when all patients have been followed for a minimum of two years.

Prognostic factors in patients age 65 and older

Another objective of this study is to determine the prognostic value of patient and disease factors upon outcomes of HCT in patients age 65 and older. After evaluating the demographics of the first 180 patients age ≥ 65 accrued to the protocol, several prognostic factors of interest (sections 3.2 and 3.3) are expected to require larger numbers of patients to achieve adequate power to detect meaningful differences in outcomes for patients in this cohort.

Based on an 80% power with an assumption of a 25% 100 day mortality in the most favorable group and a delta as indicated, the number of patients needed for each of the analyses is listed below in Table 2. The anticipated accrual for Part I was based on power calculations for a primary outcome of 100 day survival after HCT in patients 55-64 compared to 65 and older. Based upon the distribution of age (65-69 vs. 70 and over), performance score, HCT Comorbidity index¹⁴, IPSS score, and disease status in the first 180 patients enrolled, we anticipate that 700 patients will be required to complete an analysis of prognostic factors for early outcome in patients 65 and older.

Table 2: Number of patients required to test differences in 100 day mortality with 80% power for specified prognostic factors

Prognostic Factor	Number of Patients based on expected difference		
	delta =0.1	delta =0.15	delta =0.2
Age			
<70	580	246	130
≥70	183	78	41
Total	763	324	171
HCT-CI (Sorrer, et al)			
0-2	294	118	59
≥3	222	89	45
Total	516	207	104
Secondary MDS			
No	649	265	133
Yes	163	67	34
Total	812	332	167
Cytogenetics			
Good/Intermediate	376	152	76
Poor	194	79	40
Estimated Unknown/missing/not done	78	32	16
Total	648	263	132
IPSS			
Low.int-1	311	125	62
Intermediate-2/high	214	87	43
Evaluable patients	525	202	105

The above sample size calculations for prognostic factors are based on the estimated frequencies of these potential risk factors using the data accrued in the first 180 patients and a binary response of alive or dead at 100 days. The final analysis of these factors will be performed in a logistic regression model for 100 day survival or a Cox regression model for other events in the cohort of patients age 65 and older.

The distribution of relevant prognostic factors shown in sections 3.2 and 3.3, and in the power calculations shown in Table 2 will be reviewed after accrual of 500 patients age 65 and over. Adjustments will be made to the final accrual projections at that time.

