3.0 SPECIFIC AIMS

3.1. To prospectively determine the following outcomes in Medicare beneficiaries who undergo HCT for MDS and related disorders and compare these outcomes with those of non-Medicare beneficiaries, aged 55-64:

- Early (100-day) mortality
- Acute and chronic graft-versus-host disease (GVHD)
- Relapse and progression
- Disease-free survival
- Progression-free survival
- Overall survival

3.2. To prospectively determine whether there are disease- or patient-related factors that predict outcomes of HCT for MDS and related disorders in Medicare beneficiaries, including:

- World Health Organization (WHO) classification
- International Prognostic Scoring System (IPSS) score
- WHO-based Prognostic Scoring System (WPSS)
- Cytopenias
- Cytogenetics
- Primary versus secondary MDS
- Disease duration and prior therapy
- Recipient age
- Performance score
- Sorrow co-morbidity index

3.3. To prospectively evaluate what transplant characteristics are associated with outcomes of HCT for MDS and related disorders in Medicare beneficiaries, including:

- Preparative regimen
- Graft source
- GVHD prophylaxis
- Use of hematopoietic growth factors

3.4. To prospectively evaluate treatment facility characteristics associated with outcomes of HCT for MDS and related disorders in Medicare beneficiaries, including:

- Transplant volume
- Years of operation
- Academic affiliation

This study is Part 1 of a comprehensive evaluation of HCT in Medicare beneficiaries. It will evaluate outcome of allogeneic HCT, with monitoring to ensure that there is not undue early mortality in adults ≥ 65 years of age. The intent was to assemble a high quality data set of 240 patients, whose data will be analyzed to provide information pertinent to design of Part II of the study. In addition it would prospectively evaluate the effect of various disease, patient and treatment facility characteristics related to outcome. The study protocol is amended October 30, 2012 to increase the accrual to provide sufficient power to evaluate the effect of these prognostic factors on outcomes of HCT.

4.0 BACKGROUND:

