The only available therapy with the potential to cure MDS is HCT and HCT is the treatment of choice for younger patients¹¹. Prior to the introduction of RIC regimens, regimen-related morbidity and mortality limited the utility of HCT in older patients and in those with significant co-morbidities. RIC regimens now allow HCT to be offered more safely to those patients but use of HCT in the older population still remains limited. This was evident in a recent study by the CIBMTR where only 10% of patients who underwent RIC HCT were older than 65 years. In that study, age had no significant impact on outcome in multivariate analysis in a cohort of patients between 40 and 70 years.¹² The 100 day mortality rate was about 20% and the 2 year probability of survival was about 40%.

There are multiple reasons that older patients do not undergo transplantation. Older patients may have co-morbidities that compromise their ability to tolerate an intensive therapy like HCT. Some oncologists are reluctant to refer older patients for HCT, even if there are no clinical contraindications, because of perceived worse outcomes in older patients. Some transplant centers have arbitrary upper age limits for HCT candidates. Finally, some third party payers will not cover HCT in older patients until there is transformation to acute leukemia. Until recently, coverage of HCT for MDS by the US Centers for Medicare and Medicaid Services (CMS) depended on local coverage determinations¹³. CMS is the primary health insurer for most US adults 65 years of age or older. Recently, CMS made a National Coverage Determination (NCD) regarding MDS, indicating that data regarding efficacy in a CMS beneficiary population were currently insufficient but that coverage would be provided for patients enrolled in a clinical study appropriately designed to generate data necessary to make a determination about efficacy and effectiveness. This decision acknowledged that “the available evidence suggests that allogeneic HSCT for MDS is reasonable and necessary under §1862(a) (1) (E) of the Social Security Act through Coverage with Evidence Development (CED).”

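### Section 6.2.6 is inconsistent about death: followed literally, its censoring clause turns PFS into freedom from progression, which can exceed overall survival

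*Protocol*

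**What the plan says.** Protocol Section 6.2.6 defines the outcome in one sentence: "Progression-free survival: survival without increase in marrow blasts to >20%; patients without progression are censored at time of most recent marrow examination".

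The censoring clause, "patients without progression are censored at time of most recent marrow examination", is also the one used for Progression in 6.2.4.

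The neighbouring outcomes are worded differently:

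- DFS (6.2.5) names death: "Disease-free survival: survival without death or relapse". It censors survivors only: "Those who survive without recurrent or persistent disease are censored at the date of last" contact.
- OS (6.2.7): "Overall survival: Surviving patients are censored at the date of last contact".
- Relapse (6.2.3) also limits censoring to survivors, at last contact.

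Aim 3.1 lists "Progression-free survival" as an outcome separate from relapse and progression, to be compared with patients aged 55-64. Section 8.0 says: "Cumulative incidence curves will be constructed to estimate acute GVHD incidence, relapse progression rates". It also says that all secondary endpoints will be evaluated again once every patient has at least two years of follow-up.

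**The concern.** A patient who dies with marrow blasts never above 20% has not progressed. Under the censoring clause, that patient leaves the PFS analysis at the last marrow examination and the death is not counted. The same patient is an event for DFS and for OS. PFS then has the same event and the same censoring rule as Progression in 6.2.4, although aim 3.1 treats the two as different outcomes.

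What is at stake is the meaning of the reported figure. A PFS estimate should never exceed overall survival, because everyone who is progression-free is alive. An estimate that drops deaths without progression can exceed it, and it would not reflect a difference between age groups in such deaths.

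**Working it through.** **Reading the definitions side by side**

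| Section | Outcome | Death named as event? | Who is censored | When |
|---|---|---|---|---|
| 6.2.3 | Relapse | no | survivors without recurrent or persistent disease | last contact |
| 6.2.4 | Progression | no | all without progression | last marrow |
| 6.2.5 | DFS | yes | survivors without recurrent or persistent disease | last contact |
| 6.2.6 | PFS | no | all without progression | last marrow |
| 6.2.7 | OS | implied | survivors | last contact |

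Only 6.2.4 and 6.2.6 drop the survivor condition. No other section says that death without progression is a PFS event.

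**Size**

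The protocol states no PFS rate, so there is no figure of its own to reproduce. The inputs for an illustration are:

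- Section 4.0, describing a cited registry study: "The 100 day mortality rate was about 20% and the 2 year probability of survival was about 40" percent. So S(100 days) = 0.80 and S(2 years) = 0.40.
- Net 2-year progression probability p: not given in the protocol. Assumed range 10% to 60%.
- Progression and death: assumed independent, with a constant progression hazard.

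Formulas at two years:

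- Literal rule (deaths censored): 1 − p.
- Death counted as an event: S(2 years) × (1 − p) = 0.40 × (1 − p).

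For p = 0.10, the literal rule gives 1 − 0.10 = 0.90, and counting death gives 0.40 × 0.90 = 0.36.

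A simulation of 200,000 patients checks this. Death times are piecewise exponential, fitted to the two survival figures. Marrow examinations are assumed at days 28, 100, 182, 365 and 730.

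| p | Literal, formula | Literal, simulated | Death counted, formula | Death counted, simulated | Died without observed progression by 2 years (simulated) |
|---|---|---|---|---|---|
| 10% | 90% | 89.8% | 36% | 35.9% | 58.5% |
| 20% | 80% | 80.0% | 32% | 31.9% | 56.9% |
| 30% | 70% | 70.0% | 28% | 28.0% | 55.1% |
| 40% | 60% | 60.0% | 24% | 24.0% | 53.2% |
| 50% | 50% | 50.3% | 20% | 20.1% | 51.1% |
| 60% | 40% | 39.9% | 16% | 16.0% | 48.7% |

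Simulated 2-year OS is 39.9%. The literal figure exceeds OS while 1 − p > 0.40, that is, while p is below about 60%. With death counted, PFS is below OS in every row.

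At day 100 the literal rule gives (1 − p)^(100/730). For p = 10% this is 0.90^0.137 = 0.986; for p = 30% it is 0.70^0.137 = 0.952. Multiplying by 0.80 gives 0.789 and 0.762 with death counted. The simulation gives 98.6% and 95.2% against 78.8% and 76.1%, with OS at 80.0%.

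The literal expression 1 − p does not contain S. Under independence, two age groups with equal progression and unequal mortality without progression would therefore show the same literal PFS.

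**The case against.** The strongest reply is that 6.2.6 opens by describing survival without the blast increase. A patient who has died no longer meets that description, so death is already a failure. Listing PFS separately from progression in aim 3.1 supports this reading, and the censoring clause may simply have been carried over from 6.2.4. This stands in part. A reader might infer that the protocol has settled that deaths are not PFS events, and the text does not support so firm a statement. But the reply does not repair the definition: the first clause then makes a death a failure while the second censors it. The neighbouring sections show that the protocol limits censoring to survivors where it means to.

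A reader might also infer that Progression in 6.2.4 is analysed wrongly. That goes too far. Section 8.0 plans cumulative incidence curves, a method that ordinarily treats death without the event as competing. Only the wording of 6.2.4 needs alignment.

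It is also tempting to say that, even if deaths count, stopping living patients at their last marrow biases PFS downward by a stated amount. The protocol gives neither a schedule of post-transplant marrow examinations nor a completion rate, so no such amount can be supported.

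Finally, a reader might infer that the rule hides an age difference in mortality from the study. It does not. The primary 100-day mortality, DFS and OS would all show excess deaths without progression, and no sample size depends on PFS.

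**Conclusion.** The point holds as an internal inconsistency in 6.2.6 that is wrong as written. The description implies that death counts; the censoring clause removes deaths without progression. Followed literally, the outcome is net freedom from progression: 90% to 70% at two years, against 36% to 28% with death counted, for net progression of 10% to 30%.

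Those figures are an illustration. They rest on an assumed progression range, on independence of progression and death, and on a background survival of about 40%. That survival figure comes from a cited study whose title covers acute myeloid leukemia in first remission as well as MDS; it is not a design assumption of this protocol. The excess over OS shrinks as progression becomes more frequent and is gone near 60%. That the literal clause censors deaths without progression depends on none of these assumptions.

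The consequence is confined to a secondary outcome named in aim 3.1.

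**What to change.** - **6.2.6:** define the event as the first of marrow blasts above 20% or death from any cause. Censor only patients alive without progression, at the date of last contact, as 6.2.5 does for DFS.
- **6.2.4 (consistency edit):** limit censoring to survivors, and state that death without progression is the competing event in the cumulative incidence already planned in Section 8.0.

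The cost is about two sentences of wording. No new data are needed: the appended Research Database protocol already provides for a report at the time of death (its Section 4.1) and refers to death dates in study data extracts (its Section 6.2). Sample size, the primary analysis and monitoring do not change.

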The aim of this study is to prospectively examine post-HCT outcomes in CMS beneficiaries with MDS to determine whether these outcomes are similar to younger patients where the experience with HCT is more extensive and where HCT is an accepted medical therapy. The study will also evaluate patient, disease and treatment factors which might modify transplant outcomes. The objectives and methods of the study comply with the CMS-specified requirement that a “clinical study seeking Medicare payment ... pursuant to Coverage with Evidence Development (CED) must address one or more aspects” of three questions outlined in its Decision Memo (CAG-00415N). The analyses in this Study Plan are for Part 1 of this evaluation and will directly address questions 2 and 3 in that Memo and will

provide data to plan Part 2 of the evaluation, a study directly addressing question 1 in that Memo, which will compare outcomes after HCT to outcomes with non-HCT therapy.

5.0 STUDY POPULATION:

Eligible patients are persons ≥ 65 years old (or < 65 years of age and a CMS beneficiary) with myelodysplastic syndromes and related disorders, including chronic myelomonocyte leukemia (CMML), who are eligible to receive an allogeneic HCT from either an HLA-identical sibling or unrelated donor in a US transplant center and who agree to (sign Informed Consent; Appendix A) submission of comprehensive clinical data on their pre- and post-transplant clinical status and outcomes to the Center for International Blood and Marrow Transplant Research (CIBMTR). Eligibility for HCT will be according to local institutional practices. Patients younger than 65 years of age who are CMS beneficiaries are included but will be analyzed separately. The object is to capture data on the broad range of patients in whom the therapy is used; there is no exclusion for race, gender or prior therapy.

6.0 OUTCOMES:

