The primary goal of the CIBMTR Research Program is to improve the safety and effectiveness of hematopoietic cell (HC) transplantation for both donors and recipients. The NMDP database was established in 1989 and the IBMTR database was established in 1972. The Research Database contains demographic and clinical data on allogeneic related and unrelated donor and autologous HC transplants. Data are also collected on unrelated donors and their donation experiences. The data

contained in the research databases are observational data. CIBMTR does not determine which therapies are used for patients, but rather collects information regarding therapies as they are applied by transplant centers.

Secondary goals of the CIBMTR Research Program are to understand uses of hematopoietic cells for regenerative medicine or immune-based therapy, including for malignancy or infection, and to improve treatments and outcomes for those individuals who have been exposed to radiation or other chemicals that are toxic to marrow. In these cases, exposure data, organ injury data, treatment data, and outcomes data are collected.

The NMDP and the CIBMTR are the sole custodians of the data in the Research Database. The NMDP and the CIBMTR are responsible for determining who has access to the data in the Research Database (see Section 6 “Studies Involving Data in the Research Database”). The NMDP and CIBMTR are responsible for determining if and when data will be removed from the database or shared with others.

The primary purpose of the Research Database is to have a comprehensive source of observational data that can be used to study HC transplantation. A secondary purpose of the database is to have a comprehensive source of data to study marrow toxic injuries and the application of hematopoietic cells for regenerative medicine or immune-based therapy, including for malignancy or infection. Researchers whose study proposals are reviewed and approved in advance by the CIBMTR may use data for studies examining HC transplantation and its effects on recipients and donors, to study marrow toxic injury, or to study regenerative medicine or immune-based therapy, including for malignancy or infection. The following are types of studies in which these data may be included. Studies to determine:

- How well recipients recover from their transplants or cellular therapy;
- How recovery after transplantation or cellular therapy can be improved;

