4.1. Collection of Recipient Data

Recipient data are collected from pre-existing data within the recipient's medical record chart at the transplant center. Transplant Centers complete the forms at the following time-points.

Time-point	Data Collected
At registration	Name Social Security Number (U.S. participants only) Mother's maiden name City State Country of birth
At the time of transplant	Demographic data such as race and ethnicity, gender, birth date, Median household income (U.S. participants only), Education (U.S. participants only), occupation HLA typing data Pre-transplant disease-specific data such as blood counts, disease status, cytogenetics Co-existing disease at the time of transplant

	Functional status Organ function prior to transplant History of infection exposure prior to transplant Conditioning regimen HSC product manipulation
100 days, six months, one year, two year, post-transplant	Engraftment – neutrophil and platelet recovery Acute and chronic GVHD Chimerism Organ function New malignancy Disease Status Functional status Ability to return to work or school Second transplant Donor leukocyte infusion
Annually starting year three	Acute and chronic GVHD New malignancy Disease Status Functional status Ability to return to work or school Second transplant
At time of death	Primary and contributing cause of death

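### Progression and the progression part of PFS rest on one marrow-blast threshold, so leukemia documented only outside the marrow is censored as progression-free

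*Protocol*

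**What the plan says.** Protocol 6.2.4 reads "Progression: increase in marrow blasts to" more than 20%. Section 6.2.6 defines PFS as "survival without increase in marrow blasts to >20" percent. Both carry the same censoring rule: "patients without progression are censored at time of most recent marrow examination". Neither names a blood-blast, extramedullary or centre-reported criterion, and neither refers to the blast count before transplant.

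The neighbouring outcomes are wider. Relapse (6.2.3) is "disease recurrence or persistent disease for patients not in CR at transplant", and disease-free survival, DFS (6.2.5), is "survival without death or relapse". Neither is tied to the marrow or to 20%.

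On entry, section 5.0 states "Eligibility for HCT will be according to local institutional practices" and sets no blast limit. On data, section 7.0 relies on the existing registry mechanisms. The database protocol in Appendix A, section 1.3, says "CIBMTR does not determine which therapies are used for patients, but rather collects information regarding therapies as they are applied by transplant centers". Its section 4.1 sets recipient reporting at "100 days, six months, one year, two year, post-transplant" and annually from year three. Disease status is among the listed items; a marrow examination is not.

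Aim 3.1 lists relapse and progression, and PFS, among the outcomes to be compared with patients aged 55-64. Section 8.0 plans cumulative incidence curves and a further evaluation of all secondary endpoints at a minimum of two years.

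**The concern.** An event that can be met only by a marrow count needs marrow counts to be taken. Here the timing of any marrow is left to local practice. A patient whose leukemia is diagnosed from the blood, or from disease outside the marrow, may never have the qualifying examination. By the wording of 6.2.4 that patient is without progression and is censored at a marrow taken before the disease appeared. If a marrow above 20% is obtained later, the event counts but is dated late.

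The wording also requires an increase to the threshold. For a patient already above 20% just before transplant who stays above it, no such increase can be dated.

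At stake are the recorded progression incidence and the progression part of PFS. Both are outcomes named in aim 3.1, and both are carried into the two-year analysis.

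**Working it through.** The protocol gives no sample size, power or event count for progression or PFS, so there is no stated figure to reproduce. The check sets the definitions against the kinds of patient they must classify.

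**Step 1. Trace each case through 6.2.3 to 6.2.6.**

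| Case | Progression (6.2.4) | PFS (6.2.6) | Relapse (6.2.3) / DFS (6.2.5) |
|---|---|---|---|
| Marrow blasts rise above 20% | Event | Event | Can count |
| Leukemia in blood only, no qualifying marrow | No event; censored at last marrow | No progression event; censored at last marrow unless death is read as ending PFS | Can count |
| Extramedullary leukemia only, no qualifying marrow | As above | As above | Can count |
| Above 20% before transplant, falls to 20% or below, later rises above 20% | Event | Event | Can count |
| Above 20% before transplant, never falls to 20% or below | No datable increase | No datable progression event | Counts as persistent disease if not in CR at transplant |

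Rows two, three and five are the gap. It is confined to progression and to the progression part of PFS.

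**Step 2. Can the data source close the gap?** Section 4.1 of the database protocol fixes when forms are completed, not when marrows are done. Section 4.4 allows further study-specific items to be taken from medical records. That could retrieve a blast count that exists, but not a marrow that was never performed.

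**Step 3. Can row five occur?** Section 5.0 sets no blast ceiling. Section 8.1.2 records WHO class both at diagnosis and just before transplant. The background (4.0) mentions payers that withhold cover from older patients until the disease has become acute leukemia. These make entry above 20% possible. None states that such a patient is enrolled, or how many.

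**Step 4. Size.** Let s be the share of true progressions never shown by a marrow above 20%. The recorded count is (1 - s) times the true count. The documents give no value for s. For assumed values:

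- s = 5%: 1 - 0.05 = 95% recorded
- s = 10%: 1 - 0.10 = 90% recorded
- s = 20%: 1 - 0.20 = 80% recorded

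**Step 5. What an age contrast would need.** Assume a true incidence of 25% in both age groups, with s = 15% at 65 and over and s = 5% at 55-64. None of these inputs is in the documents.

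- Missed progressors kept in follow-up as non-events: 0.25 × 0.85 = 21.3% and 0.25 × 0.95 = 23.8%. The difference is 0.2375 - 0.2125 = 2.5 points.
- Missed progressors censored at day 0, the extreme form of the protocol's censoring rule: 0.2125 / (1 - 0.0375) = 22.1% and 0.2375 / (1 - 0.0125) = 24.1%. The difference is about 2.0 points.
- Equal s in both groups: no difference.

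The result moves with the censoring treatment and vanishes when ascertainment is equal, so no bias figure can be attributed to the plan.

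**Step 6. Reach.** The primary outcome is 100-day mortality (6.1.1). Table 1 and Table 2 are calculated on 100-day mortality. None uses the blast threshold.

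**The case against.** The strongest case on the other side has four parts.

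- **Other outcomes cover the same disease.** Relapse is tied neither to the marrow nor to 20%, DFS counts relapse and death, and both are compared under aim 3.1. PFS is worded as survival, so death can reasonably be read as ending it. This stands and limits the consequence. A reader might infer that leukemia outside the marrow is never counted anywhere; the definitions of relapse and DFS do not support that. They do not, however, repair progression and PFS, which are separately named outcomes.
- **Entry above 20% is not shown.** This also stands. A reader might infer that every patient entering above 20% lacks a usable event. A patient who falls to 20% or below and rises again meets the text as written, and one not in CR who never falls is already persistent disease under 6.2.3. Only the missing dating rule for that last patient remains.
- **The collection forms cannot be seen.** Section 4.1 is a summary of item headings, so it does not show that marrow blasts go uncollected. This is correct, but the point does not need it; it is enough that no marrow is scheduled.
- **A single objective threshold is a defensible registry choice, and detail belongs in an analysis plan.** In part. Baseline handling could sit in an analysis plan. The protocol itself, however, makes a marrow count the only event, and following it as written misclassifies a patient with overt leukemia outside the marrow.

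**Conclusion.** The point holds in a limited form. Progression (6.2.4) and the progression part of PFS (6.2.6) depend on one absolute marrow threshold in a registry with no marrow schedule. Leukemic progression documented only in blood or at an extramedullary site is not an event, and the patient is censored as progression-free at the last marrow. A patient above 20% before transplant who never falls to 20% or below has no datable progression event; the protocol leaves open whether any such patient enrols.

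The number of events lost is unknown. The 5% to 20% range in the working is an assumption.

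A reader might go further and infer that older or frailer patients have fewer repeat marrows, so that the age comparison is pushed toward similarity. The documents give no ascertainment rate by age, so neither the direction nor the size of such a bias is supported.

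The consequence is confined to two secondary outcomes. It is still worth correcting, because both are named comparisons in aim 3.1.

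**What to change.** In 6.2.4, count progression at the first of:

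- marrow blasts above the threshold;
- blood blasts above the same threshold;
- documented extramedullary leukemia or leukemic transformation on the disease-status report.

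Use the same definition in 6.2.6. Add one rule for a patient already above the threshold just before transplant: count progression only after a documented fall to or below it; otherwise handle the patient as persistent disease under 6.2.3.

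The cost is a change of wording in two definitions. Disease status is already reported at each post-transplant time point. Blood-blast values, if not on the existing forms, can be requested from medical records under section 4.4 of the database protocol. The downside is that some events will rest on the centre's disease-status report rather than a marrow count. Recording which criterion was met for each event would let the marrow-only version be shown alongside.
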